## Evaluation of reduced blood flow in the hands in response to cold challenge test.

Due to lack of consensus on a standard approach to noninvasive evaluation of blood flow in the hands of subjects with RP, and inadequate data to demonstrate that one modality is superior to another, we decided to take an approach where we evaluate the outcome of treatment using the cold challenge test.

## Cold challenge test.

We will standardize the cold challenge procedure as follows: We will ask subjects to refrain from caffeine for at least 4 hours prior to testing. The procedure will be performed at ambient room temperature of  $23^{\circ}\text{C} \pm 0.5^{\circ}\text{C}$  using an air conditioning or heating unit if needed. Subjects will be acclimatized for 20 minutes in the test room and standardized with subjects wearing a single layer of clothing. FLIR camera will be used to obtain thermal images from an 80 cm distance to the table top, measured from the middle of the bottom lens rim, at ambient room temperature. We will mix tap water with ice to produce a basin, with the dimensions of a length 28 cm by 21 cm wide and a depth of 14.5 cm, to create a tap water mixture with a goal temperature of  $15^{\circ}\text{C} \pm 0.5^{\circ}\text{C}$ . The basin will be filled to a measurement of 9 cm of water to allow uniform submersion and cooling around subjects hands. Subjects will then be instructed to submerge hands for one minute, timed, remove immediately once one minute submersion is complete, dry briefly with paper towels, and be instructed to sit, with proper hand placement, for imaging process using FLIR system.

# Thermography

We will use FLIR system to measure temperature and blood flow at the digits. After the cold challenge, subjects will place their hands on a setup of a carpet square measuring a length of 42.5 cm by 29.5 cm wide, placed backing side up (to reduce reflection), on a table with a grate resting on the carpet where the subject will be instructed to rest hands on. We will use 2 thresholds for use as screening when subjects do the first cold challenge without neurostimulation:

- 1. A Distal Dorsal Difference (DDD) >1°C at base line or
- 2. DDDI should > 20% at 5 min after the cold stress.

Subjects who meet the screening threshold of clinically meaningful change from baseline on the initial cold challenge will be enrolled into the study.

Week -4 (Screening). The screening visit where eligibility testing will be performed utilizing the cold challenge test, a baseline image will be taken, and physician verbal history interview performed. Subjects will begin to keep a diary of Raynaud's symptoms and number of attacks. Throughout the study, the diary will be collected at week 0, 4, 8, and 12. A diary will be provided at week -4, 0, 4, and 8. Beginning at week 0, stimulation time and occurrences with gammaCore device will be recorded in the diary along with at week 4. There is no use of gammaCore or sham at this point. Subjects continue their current standard of care treatments, except for medications prohibited while enrolled in the study.

Week 0 (Randomization). The first 32 subjects that meet screening criteria will be enrolled into the study. Diaries from Week -4 to Week 0 will be collected, and a new diary given. The 32 subjects will be randomized 1:1 to either sham device (16) or gammaCore device (16). At week 0 subjects will have a follow up image #1 taken and then be treated with sham or gammaCore -20 minutes prior to cold challenge. The first set of stimulation begins at -20 minutes (2 minutes on each side of the neck for a total of 4 minutes) and then at -4 minutes the second set of stimulation occurs (2 minutes on each side of the neck for a total of 4 minutes)

performed by the subject, monitored by the investigator, or delegated study personnel immediately after cold challenge. Using FLIR thermography to measure absolute temperature, DDD, and DDDI will be calculated from images of both hands taken at baseline, obtained by a video where images are captured at 1 min, 5 min, 10 min, 15 min and 20 minutes after the cold challenge will be measured at the dorsum and digits 2nd-4th. Images measuring the absolute temperature, DDD, and DDDI at specific regions as well as the average of all regions will be generated as a surrogate marker of blood flow.

Prior to cold challenge subjects will be trained on proper usage and administration of sham and gammaCore devices. Subjects will stimulate for 4 minutes (2 minutes each side of neck) twice a day, once in AM and once in the PM, at least 8 hours apart\_for a total of 8 minutes of stimulation daily. Subjects will begin to log the completion of stimulation and occurrences with the device, and continue recording Raynaud's symptoms and number of attacks in the diary. Subjects will continue on their current treatments with sham or gammaCore device, and continue to refrain from medications prohibited while enrolled in the study.

Week 1. Subjects will return for observation of administration of treatment with any correction if necessary and confirm that subject is documenting RP symptoms and number of attacks as well as the use of the device in the diary.

Week 2. Subjects will be contacted via telephone for a follow up call to address any device stimulation issues, make corrections if necessary, as well as confirm that subject is documenting RP symptoms and number of attacks as well as the use of the device in the diary.

Week 4 (Open Label). Subjects will return for cold challenge test and bring device back with them. Subjects will have follow up image #2 taken and then be treated with their current sham or gammaCore -20 minutes prior to cold challenge (stimulation 2 minutes each side of the neck for a total of 4 minutes) and then at time -4 minutes (stimulation 2 minutes each side of the neck for a total of 4 minutes) performed by the subject and monitored by the investigator, or delegated study personnel) immediately before cold challenge. Using FLIR thermography to measure absolute temperature, DDD, and DDDI will be calculated from images of both hands taken at baseline, obtained by a video where images are captured at 1 min, 5 min, 10 min, 15 min and 20 minutes after cold challenge will be measured at the dorsum and digits 2nd-4th. Images measuring the absolute temperature, DDD, and DDDI at specific regions as well as the average of all regions will be generated as a surrogate marker of blood flow.

Following Week 4 cold challenge sham subjects will be placed on active treatment with gammaCore so that all subjects will be on open label active treatment at Week 4. All subjects will be retrained on proper usage and administration of gammaCore. Subjects will stimulate for 4 minutes (2 minutes each side of neck) twice a day, once in AM and once in the PM at least 8 hours apart, for a total of 8 minutes of stimulation daily. The diary from week 0 to 4 will be collected and subjects will be provided a new diary to continue recording the completion of stimulation and occurrences with the device, and Raynaud's symptoms and attacks. Subjects will continue their treatments with the gammaCore device and continue to refrain from medications prohibited while enrolled in the study.

Week 8. Subjects return for cold challenge test and bring device back with them to be returned. The diary from week 4 to 8 will be collected and subjects will be provided a new diary to record their Raynaud's symptoms and number of attacks in. Subjects will have follow up image #3 taken and then will be treated with gammaCore -20 minutes prior to cold challenge (stimulation 2 minutes each side of the neck for a total of 4 minutes) and then at time -4 (stimulation 2 minutes each side of the neck for a total of 4 minutes, performed by the subject and monitored by the investigator, or delegated study personnel) immediately before cold challenge. Using FLIR thermography absolute temperature, DDD, DDDI will be calculated from images of both hands taken at baseline, obtained by a video where images are captured at 1 min, 5 min, 10 min, 15 min and 20 minutes after cold challenge will be measured at the dorsum and digits 2nd-4th. Images measuring the absolute temperature, DDD, and DDDI at specific regions as well as the average of all regions will be generated as a surrogate

marker of blood flow. Study will end at Week 12 with the possibility of long term open label extension that will be decided later.

Week 12. Subjects will return to turn in completed diary.

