## The Specific Sequential Aims of this application are as follows:

- Aim 1: Evaluate the clinical efficacy of gammaCore (16 subjects) vs sham device (16 subjects) in preventing vasospasm in 32 PRP subjects.
- Aim 2: Evaluate the clinical efficacy of gammaCore (16 subjects) vs sham device (16 subjects each) on Raynaud's symptoms and chronic PRP in 32 subjects with chronic PRP for four weeks using Raynaud's condition score.
- Aim 3: Observe response rates in an open label fashion after sham subjects are transitioned to gammaCore.

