#### 2. EXPERIMENTAL DESIGN

# Study population

We will consent 40 subjects with Raynaud's phenomenon seen previously at the University of Toledo Medical Center (UTMC). After meeting the screening requirements 32 subjects will be randomized 1:1 to sham device (16) or gammaCore device (16). The sample size calculation is based on the minimum recommended number of samples to detect a difference in the outcome of the intervention with a confidence level of 90%, and margin of error of 10%. Each individual will sign an informed consent that is approved by the IRB at UTMC before participating in this study. The research protocol will be explained in detail and in lay language to each subject. We will exclude subjects who currently smoke, subjects with digital ulcers, subjects who are less than 18 years of age, subjects with pulmonary hypertension, and subjects who are receiving vasodilators such PDE-5 inhibitors, prostacyclin, nitroglycerine, or other nitric oxide derivatives. Subjects who are using Calcium Channel Blockers (CCBs) will be allowed to continue their medication, however, should be on stable therapy at least 4

weeks prior to study initiation. We will also exclude pregnant women from these studies, which will be evaluated at screening with a urine dipstick pregnancy test. Subjects who have had neck surgery in the past year (i.e. carotid endarterectomy) or that have a carotid bruit, will be excluded as well. GammaCore device cannot be used in those that have a history of metallic device such as a stent, bone plate, or bone screw implanted at or near their neck. Any history or current evidence of any condition, therapy, or other circumstances which, in the opinion of the investigator, might pose an unacceptable risk to the subject (i.e. unable to comply with requirements of the trial, or likely to interfere with the subjects participation for the full duration of the trial).

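### No entry rule asks for recent Raynaud's attacks, and the run-in diary goes unused, so subjects with a quiet run-in can dilute the Aim 2 symptom comparison

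*Combined protocol and SAP*

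**What the plan says.** **Who is approached.** Under Study population, "We will consent 40 subjects with Raynaud's phenomenon seen previously" at the centre, of whom 32 are to be randomised, 16 per arm. The exclusions cover smoking, digital ulcers, age, pulmonary hypertension, vasodilators, pregnancy, neck surgery or implants, and investigator judgement. Subjects on stable calcium channel blockers may continue them. No item concerns how often attacks occur.

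**What admits a subject.** The Thermography section gives two screening thresholds joined by an or: DDD above 1°C at baseline, or DDDI above 20% five minutes after the cold stress. Then: "Subjects who meet the screening threshold of clinically meaningful change from baseline on the initial cold challenge will be enrolled into the study". A physician takes a verbal history at the same visit, with no criterion attached to it.

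**What happens to the run-in diary.** Subjects start recording symptoms and attacks at Week -4. At the randomisation visit, "Diaries from Week -4 to Week 0 will be collected, and a new diary given". The first 32 to satisfy the screening criteria are randomised, and the diary is not among those criteria.

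**What Aim 2 needs.** It compares gammaCore with sham "on Raynaud's symptoms and chronic PRP in 32 subjects with chronic PRP for four weeks using Raynaud's condition score". Sham subjects move to gammaCore after the Week 4 cold challenge.

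**The concern.** The thermographic threshold suits Aim 1, which concerns the response to a cold challenge. Aim 2 concerns daily symptoms in the same 32 subjects, and passing a thermographic test does not show that a subject currently has attacks. The plan calls the Aim 2 population chronic PRP but does not tie that term to recent attacks. Some subjects may be well controlled on a permitted calcium channel blocker or other continuing care. Recruitment is confined to one season, which is not said to be a cold one.

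A subject with few or no attacks on either device adds little or nothing to the difference between arms, yet takes one of 32 places. Because everyone is on active treatment from Week 4, Weeks 0 to 4 are the only sham-controlled symptom data, and information lost there cannot be recovered later.

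**Working it through.** **1. The plan's own figure.** The stated basis for 32 is 90% confidence and a 10% margin of error. The usual precision formula gives n = z²p(1−p)/e² = 1.645² × 0.25 / 0.01 = 67.6, so 68. With a finite-population correction at 40 it gives 67.6 / (1 + 66.6/40) = 25.4, so 26. Neither is 32. The plan states no effect size, SD or power, so there is no Aim 2 power figure to reproduce. That is a separate matter and does not decide this point.

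**2. How little margin 16 per arm leaves.** At two-sided 0.05 (sidedness assumed), 80% power needs a difference of (1.960 + 0.842) × √(2/16) = 0.99 SD. If a share f of each arm cannot benefit and the SD is unchanged, the mean effect becomes 0.99(1−f), and power = Φ(0.99(1−f)√8 − 1.96).

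| Attack-free per arm | f | Power |
|---|---|---|
| 0 of 16 | 0 | 80% |
| 2 of 16 | 12.5% | 69% |
| 4 of 16 | 25% | 56% |
| 8 of 16 | 50% | 29% |

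**3. An attack-count model.** All inputs here are assumptions except 16 per arm and the 0.05 level.
- Each subject's mean attacks per four weeks is drawn from a gamma distribution (shape 2, scale 5, mean 10), or is zero with probability f.
- Run-in count: Poisson(mean). Weeks 0 to 4 count: Poisson(mean) on sham, Poisson(0.5 × mean) on active.
- Test A: two-sample t-test on change from run-in (4,000 trials per setting; simulation standard error about √(0.66 × 0.34 / 4000) = 0.7 points).
- Test B: Weeks 0 to 4 count adjusted for the run-in count.

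| Attack-free share f | A: change from run-in | B: adjusted for run-in |
|---|---|---|
| 0% | 83% | 95% |
| 10% | 78% | 93% |
| 25% | 66% | 85% |
| 40% | 53% | 74% |

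Repeat runs agreed within about 2 points. Adjustment raises power at every share but does not stop the decline. Requiring at least one run-in attack, and still filling 32, gives about 85% with test A.

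**4. How likely a quiet run-in is.** The documents give no attack rates. Under a Poisson assumption, the chance of no attacks in 28 days is exp(−4 × weekly rate): 37% at 0.25 attacks per week, 14% at 0.5, 1.8% at 1, and below 0.1% at 2. The problem matters mainly if mild or well-controlled cases are enrolled.

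**5. Can 40 consented subjects fill 32 places?** In the model in step 3, a subject with active disease still records a zero run-in with probability (1/6)² = 1/36 = 2.8%. The chance of at least one run-in attack is therefore (1−f) × 35/36. The third column is the binomial chance that at least 32 of 40 qualify, before any thermographic failures.

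| f | Chance a subject qualifies | At least 32 of 40 | Consents needed on average |
|---|---|---|---|
| 10% | 0.9 × 35/36 = 0.875 | about 94% | 32/0.875 = 37 |
| 25% | 0.75 × 35/36 = 0.729 | about 21% | 32/0.729 = 44 |
| 40% | 0.6 × 35/36 = 0.583 | under 1% | 32/0.583 = 55 |

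**The case against.** **Stronger readings that the documents do not support.**
- *Entry rests on thermography alone.* A reader might infer this from the enrolment sentence. A Raynaud's diagnosis, the exclusions and an investigator-judgement clause also apply. What is missing is any requirement for recent attacks or symptoms.
- *A subject with a quiet run-in has no room to improve.* That holds for change in attack count from run-in. Aim 2 names Raynaud's condition score, whose scale and timing the plan does not define, so a floor is an assumption there. Such a subject may also have attacks in Weeks 0 to 4. The comparison is diluted, not empty.
- *The comparison is biased.* Randomisation follows the run-in, so quiet subjects fall into either arm by chance. The harm is lost power.

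**The case against acting.** The attack-free share in the simulation is put in by hand, and the 25% and 40% rows have no support in the documents. The endpoint and test are also assumed: the Statistical analysis section covers only temperature, DDD and DDDI. Much of the low power in column A comes from the change-score test. With the run-in count as a covariate, 25% attack-free gives about 85%, slightly above the 83% of the change score with none attack-free. A subject with a positive thermogram and a quiet diary is fully informative for Aim 1, so excluding them costs that aim. The study is a proof of concept with no stated Aim 2 power target.

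**What stands.** All of this limits the size of the problem, and the covariate argument belongs in the fix. It does not remove the gap: even with adjustment, power falls from about 95% to 74% across the range, and the diary that could prevent it is collected before randomisation.

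**Conclusion.** The point holds as a matter of power, and a change is worth making. Nothing in the plan requires recent attacks or symptoms, and the run-in diary is available but unused.

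The size cannot be fixed from the documents. It is about 5 points of power at 10% attack-free (83% to 78%), 17 at 25% and 30 at 40%, for an attack-count outcome tested by change from run-in. This assumes a mean of 10 attacks per four weeks, a true halving on active treatment, and no attacks at all in the attack-free group. The dilution calculation in SD units shows the same direction. If most subjects have an attack a week or more, the loss is small.

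**What to change.** 1. **Entry.** At Week 0, before randomisation, check the Week -4 to Week 0 diary against a minimum level of activity. At least one recorded attack is an example; the sponsor should set and justify the level.
2. **Analysis.** Specify that the Week 0 to 4 symptom outcome is compared between arms with adjustment for the run-in diary value, recorded in the same way in both periods.

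**Cost.** One eligibility line and one analysis sentence, using a diary already planned. There will be more screen failures and a slightly narrower population for Aim 1 as well as Aim 2. The 8 spare subjects must also cover thermographic failures. They probably suffice at about 10% attack-free, but not at 25% or more. There, the sponsor would have to consent more than 40, or leave entry unchanged and rely on the adjustment alone, accepting about 85% power at 25% and 74% at 40% in the same model.

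Restricting the Aim 2 analysis set to subjects with a run-in attack is not a useful substitute. At 25% attack-free it moves the change-score test only from 66% to 70%, and it adds nothing once the run-in value is adjusted for (about 85% either way).

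### The Week 4 move to open label can expose allocation before the randomised thermograms are measured and before the Week 0–4 diary is handed in

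*Combined protocol and SAP*

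**What the plan says.** The Specific Sequential Aims set Aims 1 and 2 as sham-controlled comparisons of 16 versus 16 subjects, and Aim 3 as an open-label observation after sham subjects move to gammaCore.

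Under Thermography, the Week 4 (Open Label) entry runs in this order:

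1. All subjects attend: "Subjects will return for cold challenge test and bring device back with them".
2. They stimulate with their allocated device, undergo the cold challenge and are imaged, with frames "obtained by a video where images are captured at 1 min, 5 min, 10 min, 15 min and 20 minutes after cold challenge".
3. The switch follows: "sham subjects will be placed on active treatment with gammaCore so that all subjects will be on open label active treatment at Week 4".
4. Both arms are then trained again: "All subjects will be retrained on proper usage and administration of gammaCore".
5. Diary handover comes last: "The diary from week 0 to 4 will be collected and subjects will be provided a new diary".

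The visit entries, the section on demonstrating the effect of treatment, and Statistical analysis list the quantities to be calculated (absolute temperature, DDD, DDDI), the frame times and the sites (back of the hand, second to fourth digits). None of them says who measures the images, when, or whether that person is unaware of the arm. From the Abstract on, no text describes subjects, trainers, monitoring staff or image readers as masked. No rule requires Week 0 and Week 4 data to be completed or locked before the switch.

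**The concern.** A sham protects a comparison only while allocation stays hidden from those who measure or report the outcome. The Week 4 step acts on one arm by name, so someone at the visit must know who had sham. It takes place at each subject's own visit, not after all randomised data are in. The frames come from stored video and can be measured at any later time.

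Two randomised outcomes are exposed. For Aim 1, whoever places the regions on the Week 0 and Week 4 frames may know the arm. For Aim 2, the self-reported record of symptoms and attacks for Weeks 0–4 may still be with the subject when allocation becomes known. Either could shift results towards the hypothesis, and no later controlled period exists in which to check them.

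**Working it through.** **Order of steps against what is protected.**

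- *Capture of Week 4 images.* The switch is timed by "Following Week 4 cold challenge sham subjects will be placed on active treatment with gammaCore", and imaging also follows the challenge. The imaging text comes first, so capture plausibly precedes the switch.
- *Measurement of images.* No time, reader or masking is stated for Week 0 or Week 4, so measurement with knowledge of arm is possible.
- *Week 0–4 diary.* It is listed after the switch and retraining. If the steps are followed in the written order, the diary is still with the subject when allocation may be disclosed.
- *Device handling.* Both arms bring devices and both are retrained. The text does not say that gammaCore subjects also receive a replacement, or that prior allocation is withheld.
- *Latitude in measurement.* Frame times and sites are fixed. What is left to judgement is where a region is placed within a named site.

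**Scale of a possible bias.** The plan gives no figure for reading error and no SD for DDD or DDDI, so a bias cannot be expressed in degrees or per cent. It is shown in SD units instead.

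Inputs: 16 per arm (Study population); significance at P < 0.05 by t-test (Statistical analysis). Two-sided testing is an assumption, because sidedness is not stated. The shift b is also an assumption. The plan names one-way ANOVA as well; with two groups it is equivalent to the two-sided t-test.

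With no true effect and a reading shift of b SD in favour of gammaCore:

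- standard error of the difference in SD units = √(1/16 + 1/16) = √0.125 = 0.354
- noncentrality = b / 0.354, with 30 degrees of freedom and critical value 2.042
- false-positive rate = P(|noncentral t| > 2.042)

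| Assumed shift b | Noncentrality | False-positive rate | Part favouring gammaCore |
|---|---|---|---|
| 0 | 0 | 5.0% | 2.5% |
| 0.1 SD | 0.28 | 5.9% | 4.6% |
| 0.25 SD | 0.71 | 10.5% | 10.1% |
| 0.5 SD | 1.41 | 27.8% | 27.7% |

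For comparison, the difference detectable with 80% power at this size is about (1.960 + 0.842) × 0.354 = 0.99 SD. The largest assumed shift is about half of that, the smallest about a tenth.

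**The case against.** The other side has a substantial case.

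- *The switch need not reveal the arm.* All subjects bring the device and all are retrained on gammaCore. A reader might infer that the Week 4 visit necessarily tells each subject what they had. The text does not say so; it simply does not prevent it.
- *The images may be measured in time.* A reader might infer that they are read after unmasking. The protocol gives no time, and its measurement paragraph comes before the switch paragraph. What stands is that no rule secures this.
- *Little is left to judgement.* A reader might suppose that frames can be chosen. They cannot: times and sites are fixed and an average of all regions is also required. Region placement remains.
- *Aim 3 is open label by declaration.* Former sham subjects may expect more than those who continue on gammaCore, but knowledge of current treatment is the stated design, and no between-group test is assigned to Aim 3. This limits interpretation and is not an error.
- *The diary is mostly complete by then.* The Week 1 visit and Week 2 call confirm that it is being filled in. Late handover matters only if entries are added or changed that day, and nothing shows that they would be. Aim 2 also names the Raynaud's condition score, which the visit entries do not mention, so how far the diary carries that endpoint is not stated.
- *Staff may know the arm from Week 0.* They train subjects and monitor stimulation. A change at Week 4 does not alter that, so coded image files matter more than the handover.

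These arguments narrow the point. They do not supply the missing protection for measurement or the missing order for the diary.

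**Conclusion.** The point holds in this limited form. As written, allocation can be known when regions are placed on the Week 0 and Week 4 frames and while the randomised-period diary is still with the subject. The documents do not show that it will be known, or that any bias will follow.

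The size is unknown. The range of 5.9% to 27.8% rests wholly on assumed shifts of 0.1 to 0.5 SD and a two-sided test. It should not be read as an estimate of this trial's error rate; with times and sites fixed, nothing in the documents shows that the larger shifts are plausible.

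The conclusion also rests on the protocol text from the Abstract on. A masking label in the pages before it cannot be excluded, but the order of the Week 4 steps and the conditions of image measurement would still need to be stated. The change is worth making because it protects the only sham-controlled comparison at small cost.

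**What to change.** In the Week 4 entry and in Statistical analysis:

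1. Collect the Week 0–4 diary on arrival, before any switch or disclosure.
2. Take back every subject's device and issue every subject a gammaCore, handled identically in both arms, without disclosing prior allocation.
3. Store Week 0 and Week 4 frames under codes that hide subject, arm and visit. Have the person who would measure them anyway do so from the coded files, and lock the values before allocation is opened to that person.
4. State who is masked, and from when, including the staff who train subjects and monitor stimulation.
5. Report Aim 3 as descriptive, noting that expectation may differ between former sham and continuing gammaCore subjects.

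The cost is re-issue of devices to all subjects, file coding and slightly later unmasking. Subjects already bring their devices and are all retrained, and the existing reader can be used. Someone other than that reader must hold the codes; the protocol does not name such a person, but the task is small. Treatment, visit schedule and sample size do not change.
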